9.2.1 Original statistical plan (prior to July 2019 amendment)

9.2.1.1 Sample size with power justification

A total of 126 patients will be needed to accrue 120 randomized eligible cases. The study seeks to establish an improvement in the primary endpoint, which is defined as a 67% improvement in median progression-free survival (PFS) from 6 months in the control arm (Arm B) to 10 months in the experimental arm (Arm A). The study is designed to have 90% power for this 40% reduction in the hazard rate with 120 eligible patients and 105 PFS events (at full information) which are expected to occur with 30 months of accrual at 4 patients per month and 12 additional months of follow-up, using a log-rank test at a one-sided significance level of 0.10. Under exponential distributions the hypothesized reduction corresponds to 1-year progression-free survival of 44% in Arm A versus 25% in Arm B.

9.2.1.2 Analysis plan including plans for formal interim analysis

The primary analysis set will include all randomized eligible patients. Progression-free survival (PFS) is defined as time from randomization to documented progression or death without progression. Patients without documented progression or death reported will be censored at the time of the last documented disease evaluation. In the secondary analyses, overall survival (OS) is defined as time from randomization to death from any cause, censoring cases who are alive at the date of last contact. Kaplan-Meier estimates will be used for event-time distributions. PFS and OS by arm will be compared using one-sided stratified log-rank tests. Stratified Cox's proportional hazards models will be used to estimate hazard ratios. Response rate (complete response or partial response) and toxicity are also secondary endpoints.

Response rate will be analyzed using a Fisher's exact test at a one-sided significance level of 0.10.

Patient demographics and disease characteristics will be compared using two-sample t-tests or Fisher's exact tests as appropriate. We will also conduct exploratory subset analyses with respect to PFS, OS, and response rate to evaluate the prognostic significance of Ki-67 with regard to these clinical endpoints.

Toxicity will be evaluated among all treated patients regardless of eligibility and interim analyses of toxicity are performed twice yearly for all ECOG-ACRIN studies. With 63 patients per arm, the study will have sufficient precision to provide 90% confidence interval on toxicity that will be no wider than 22%. For rare toxicities with 2% true probability, there will be 75% probability of observing one or more toxicities in either treatment arm. For rare toxicities with 3% true probability, there will be 85% probability of observing one or more toxicities on either treatment arm. Formal comparison of toxicity rates between the arms is not a goal of this trial and the sample size will provide sufficient power for detecting only relatively large differences in adverse events.

This study will include one interim analysis of PFS for efficacy at 20 months (10 months before the projected end of the accrual period, which should correspond to 57 failures under the alternative hypothesis or 50% information time). A log rank test using an O'Brien-Fleming boundary will be conducted and under the alternative hypothesis there is probability of 0.42 that the efficacy boundary will be crossed. Regarding futility, if at the interim analysis the estimated hazard ratio for experimental/control is ≥ 1 the study will be reported as negative. If the estimated hazard ratio is less than 1 but the efficacy boundary is not crossed, the study will have its final analysis at 42 months of study time or 12 months post end of accrual. Results of the interim analysis will be presented to the ECOG-ACRIN Data Safety Monitoring Committee (DSMC) when appropriate.

9.3 Feasibility

G3 gastroenteropancreatic neuroendocrine carcinomas are rare, accounting for approximately 11% of all neuroendocrine neoplasms. As such, a randomized trial in this patient population has never been conducted. Given the lack of data available and the rarity of this disease, the Neuroendocrine Task Force is committed to pursuit of a clinical trial in this patient population and this trial will be heavily promoted throughout the National Clinical Trials Network cooperative groups. As it is a rare disease, intergroup participation will be required to meet accrual goals. As there is no precedent providing an estimate of patients available for this trial, tumor registry and database data have been collected from

many members of the Neuroendocrine Task Force for a preliminary estimate of feasibility. As all cooperative group sites would be able to participate, we anticipate that a greater number of patients than listed below will be available for the study.

9.4 Safety monitoring

Interim analyses of toxicity are performed twice yearly for all ECOG-ACRIN studies. Reports of these analyses are sent to the ECOG-ACRIN Principal Investigator or Senior Investigator at the participating institutions. Expedited reporting of certain adverse events is required, as described in Section [5.2](#).

9.5 Study Monitoring

This study will be monitored by the ECOG-ACRIN Data Safety Monitoring Committee (DSMC). The DSMC meets twice each year. For each meeting, all monitored studies are reviewed for safety and progress toward completion. When appropriate, the DSMC will also review interim analyses of outcome data. Copies of the toxicity reports prepared for the DSMC meetings are included in the study reports prepared for the ECOG-ACRIN group meeting (except that for double blind studies, the DSMC may review unblinded toxicity data, while only pooled or blinded data will be made public). These group meeting reports are made available to the local investigators, who may provide them to their IRBs. Only the study statistician and the DSMC members will have access to interim analyses of outcome data. Prior to completion of this study, any use of outcome data will require approval of the DSMC. Any DSMC recommendations for changes to this study will be circulated to the local investigators in the form of addenda to this protocol document. A complete copy of the ECOG-ACRIN DSMC Policy can be obtained from the ECOG-ACRIN Operations Office - Boston.

Rev. Add3
Rev. Add4

9.6 Gender and Ethnicity (Revised for July 2019 amendment)

Based on previous data from ECOG ACRIN neuroendocrine trials the anticipated accrual in subgroups defined by gender and race is:

Ethnic Category	Gender		
	Females	Males	Total
Hispanic or Latino	0	2	2
Not Hispanic or Latino	34	44	78
Ethnic Category: Total of all subjects	34	46	80

Racial Category			
American Indian or Alaskan Native	0	0	0
Asian	0	2	2
Black or African American	5	8	13
Native Hawaiian or other Pacific Islander	0	0	0
White	29	36	65
Racial Category: Total of all subjects	34	46	80

The accrual targets in individual cells are not large enough for definitive subgroup analyses. Therefore, overall accrual to the study will not be extended to meet individual subgroup accrual targets.

9.7 Correlative Studies Statistics

9.7.1 Pathology samples will be collected from all eligible patients. Ki-67 will be determined using immunohistochemical analysis and will be reported as a percentage ranging from 0-100%, based on counting at least 500 tumor cells in the regions with the highest labeling rate ("hot spots")

The primary analysis of Ki-67 will be to evaluate the interaction, if any, between Ki-67 as a continuous measure and treatment. Cox regression or logistic regression, as appropriate, will be used to identify whether the treatment effect varies by Ki-67 for PFS, OS, and RR. Subsequent analyses to identify "optimal" cutpoints from continuous Ki-67 measurement are considered exploratory.

Receiver operating characteristics (ROC) analysis will also be performed to determine the optimal cutoff value in Ki-67 that defines patients with prolonged OS, where prolonged OS is defined as survival of at least 12 months. Hence in these analyses, survival will be considered as a binary endpoint. This optimal cutoff will serve for differentiating patients with features that are clinically more consistent with a well differentiated non-small cell gastrointestinal neuroendocrine tumor from the analysis set.

For the series of Ki-67 values observed in the data, Youden's index will be calculated and with the highest index we will identify the threshold that minimizes the false positive and false negative rates for best detecting prolonged OS. Optimal cutoff values of Ki-67 with respect to response to temozolomide and capecitabine will be determined in similar exploratory manner but the analysis will differ in that we will only include patients whose Ki-67 and response to temozolomide and capecitabine are available. Response to temozolomide and capecitabine is defined as complete response or partial response defined by RESIST 1.1 following initiation of therapy.

Concordance between Ki-67 measured centrally versus registering institutions' pathology assessments will also be investigated and reported. Intra-class correlation will be calculated to assess agreement amongst the two continuous measures.

We will also assess the prognostic significance of well differentiated versus poorly differentiated non-small cell gastroenteropancreatic neuroendocrine tumors in relationship to survival and response to treatment in a similar manner, via Cox proportional hazard models for time to event endpoint and logistic regression for objective response.

Rev. 2/17

Rev. Add3

10. Imaging Study Submissions

Baseline standard of care images including a CT of the chest, abdomen and pelvis will be obtained for each patient. If octreotide scan (SPECT or SPECT/CT) , ⁶⁸Ga-PET scans and ¹⁸F-FDG PET scans are done, it is requested that images be submitted. Subsequent CT scans of the chest, abdomen and pelvis will be obtained every two months. Additional octreotide scans, ⁶⁸Ga-PET scans and ¹⁸F-FDG PET scans may also be obtained per physician discretion. As the radiographic characteristics of G3 gastroenteropancreatic neuroendocrine carcinomas have not been extensively studied, building of a centralized bank of images will generate a resource upon which researchers may draw to ask further radiographic questions regarding this tumor type. This data set of serial images from approximately 80 patients with G3 gastroenteropancreatic neuroendocrine carcinomas will serve as one of the largest NEC image banks. In the future, the de-identified image bank may be used for additional research, such as retrospective reviews of disease or software validation. Patient identifiers will never be included in future research and no patients will be named in publications related to future research.

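### The exploratory Ki-67 cut-offs are chosen by maximising Youden's index on the same data, with no interval and no optimism correction, yet the OS cut-off is given a classifying role

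*Combined protocol and SAP*

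**What the plan says.** All of this is in Section 9.7 (9.7.1).

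- **Status of the analyses.** "The primary analysis of Ki-67 will be to evaluate the interaction, if any, between Ki-67 as a continuous measure and treatment". Cox or logistic regression is used as appropriate for PFS, OS and response rate. Then: "Subsequent analyses to identify 'optimal' cutpoints from continuous Ki-67 measurement are considered exploratory".
- **OS cut-off.** A ROC analysis is run in which "prolonged OS is defined as survival of at least 12 months", followed by "Hence in these analyses, survival will be considered as a binary endpoint".
- **Selection rule.** Youden's index is worked out at each observed Ki-67 value, and the choice is its maximum: "with the highest index we will identify the threshold that minimizes the false positive and false negative rates".
- **Response cut-off.** It is found in a similar exploratory way, restricted to patients with both Ki-67 and response to temozolomide and capecitabine available.
- **Use.** The OS cut-off is given a purpose: "This optimal cutoff will serve for differentiating patients with features that are clinically more consistent with a well differentiated" (the sentence then names the tumor type).

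The section names no interval, resampling or validation for either cut-off. It also gives no rule for patients alive but followed for less than 12 months in the OS cut-off.

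**The concern.** A cut-off that maximises an accuracy index over every observed marker value fits the noise in the sample as well as the signal. Sensitivity, specificity and Youden's index computed in those same patients are then too favourable, and the location of the maximum can move a long way from sample to sample. With 78 patients, and about 39 for response in Arm A, both effects are large.

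The reader of the trial report is the one at risk. Section 1.7 says a later phase III study is unlikely and expects the results to be practice changing, so external validation may not follow. A single Ki-67 value reported without an interval, and described as one that will separate patients, could be read as far firmer than it is.

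**Working it through.** **1. The plan's own figures.** Section 9.7 gives no sample size, precision or accuracy for the cut-off analysis. The nearest stated figures, which fix the number of patients and the follow-up, are in Section 9.2: 71 PFS events, 80% power, HR 0.60, one-sided 0.10, 78 eligible patients (39 per arm), 75 + 7 months. They reproduce:

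- Schoenfeld events: 4 × (1.2816 + 0.8416)² / (ln 0.60)² = 4 × 4.508 / 0.2609 = 69.1, rounded up to 70 (stated 71).
- Power with 71 events: 0.808.
- Expected events at month 82, with uniform accrual and exponential medians of 10 and 6 months: 71.4.

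**2. Share with prolonged OS.** The documents quote a median OS of 10 months (Section 1.1) and 15 to 19 months (Section 1.3). If survival is exponential, S(12) = 0.5^(12/median), which gives 0.435 for 10 months, 0.574 for 15 and 0.645 for 19.

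**3. Optimism of the maximum index.** J(c) = sensitivity(c) + specificity(c) − 1, maximised over the observed values. Assumptions: a binormal marker, with the AUC as listed. There were 8,000 runs per setting. The OS rows use S(12) = 0.435. The response rows assume a 33% response rate, the figure quoted for second-line temozolomide-based therapy in Section 1.4.

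| Setting | AUC | Mean apparent J | Mean true J at chosen cut | Difference |
|---|---|---|---|---|
| OS, n=78 | 0.50 | 0.13 | 0 | 0.13 |
| OS, n=78 | 0.60 | 0.25 | 0.12 | 0.12 |
| OS, n=78 | 0.65 | 0.31 | 0.19 | 0.12 |
| OS, n=78 | 0.70 | 0.38 | 0.27 | 0.11 |
| OS, n=78 | 0.75 | 0.45 | 0.34 | 0.10 |
| Response, n=39 | 0.50 | 0.19 | 0 | 0.19 |
| Response, n=39 | 0.65 | 0.36 | 0.18 | 0.18 |
| Response, n=39 | 0.70 | 0.43 | 0.25 | 0.17 |

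Differences are taken before rounding. With S(12) = 0.645 the n=78 differences run from 0.11 to 0.14.

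**4. Location of the cut-off.** Assumptions: Ki-67 uniform on 20 to 100, a true step at 55 (the cut used in the retrospective series of 305 patients in Section 1.2), OS hazard ratio 1.8 above against below it, n=78, every patient followed for 12 months. There were 8,000 runs per setting.

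| Median OS (months) | Median chosen cut | 95% range |
|---|---|---|
| 10 | 54.9 | 33 to 84 |
| 15 | 55.6 | 32 to 87 |
| 19 | 56.5 | 31 to 89 |

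Mean optimism in these runs was 0.10 to 0.12. A smooth Ki-67 effect instead (hazard ratio 2 per 40 points) gave an SD of 12 to 13 points and a 95% range of about 35 to 87.

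**5. Patients not classifiable at 12 months.** At month 82, those enrolled after month 70 have less than 12 months of potential follow-up: 78 × 5/75 = 5.2 patients. The expected number alive and censored before 12 months is (78/75) × the integral of S(u) from 7 to 12 months: 2.7, 3.4 and 3.7 for medians of 10, 15 and 19 months. Five months later it is zero apart from loss to follow-up. With an assumed 0 to 10% annual loss, excluding these patients, counting them as survivors or counting them as deaths moved the mean cut-off by about 1 Ki-67 point and the mean index by less than 0.05. Inverse-probability-of-censoring weights gave the same cut-off as dropping them in about 98% of runs.

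**The case against.** The strongest reply is that the plan already puts these searches in their place. They are called exploratory, the primary Ki-67 question is answered by a continuous interaction model that handles censoring, and well versus poorly differentiated histology has its own Cox and logistic models. The cut-off has no part in eligibility, treatment or the PFS test. All of this stands, and it keeps the point minor. It does not remove the point, because an exploratory estimate still needs a measure of its uncertainty, and the sentence on the cut-off's use goes further than the label allows.

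Three stronger readings are tempting, and the documents do not support them.

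- **That the plan mishandles censored patients or discards long survivors.** Section 9.7 is silent on patients censored before 12 months; it neither drops them nor codes them as deaths. Section 5.6 follows survival for 5 years from randomization. Month 82, and the interim at about month 48, are dates for the PFS analysis in Section 9.2, and nothing ties the ROC analysis to either. Even on a 48-month snapshot, dropping these patients and weighting gave the same cut-off in 93 to 95% of runs.
- **That the cut-off itself is overstated.** The chosen value centres near the truth (median 55 to 56.5 for a true 55). The apparent accuracy is inflated, and the location is imprecise.
- **That the cut-off is the trial's answer on which patients differ biologically.** That role belongs to the interaction and histology models.

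**Conclusion.** The concern holds as a minor one. Choosing each cut-off on the same data with no correction would inflate Youden's index by about 0.10 to 0.14 at n=78 and about 0.17 to 0.19 at n=39. A marker with no information would still show a mean index of 0.13 to 0.14 and 0.19 respectively. A true cut of 55 could be reported as almost anything from about 30 to 87. The wording that the OS cut-off will serve to separate patients is not supportable at that precision.

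The sizes rest on assumptions that the documents do not give: the Ki-67 distribution, the AUC range, the strength of the Ki-67 effect on OS, exponential survival, uniform accrual, and a 33% response rate in Arm A. The direction of the optimism does not depend on them; it appeared in every setting tried. Censoring before 12 months is a small gap in the text, closed by timing the analysis. The primary PFS comparison and the primary Ki-67 interaction analysis are unaffected.

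**What to change.** Amend Section 9.7 as follows.

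1. Report each Youden cut-off, for 12-month OS and for response, with a bootstrap confidence interval in which the whole search is repeated in every resample.
2. Report bootstrap optimism-corrected sensitivity, specificity and Youden index beside the apparent values.
3. Describe the OS cut-off as hypothesis-generating, in place of the statement that it will serve to differentiate patients.
4. Run the OS cut-off analysis once every eligible patient has 12 months of potential follow-up, and state how patients lost before 12 months are treated. A time-dependent ROC with censoring weights is an option, but it changes little here.

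This is a cheap improvement: new wording and slightly more analysis, with no new patients or data. Its price is less favourable reported accuracy, a wide interval, and an OS cut-off about five months after month 82 if the trial runs to its planned end.

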2.3 Laboratory Research Objectives

2.3.1 To assess the impact of each treatment regimen on PFS, RR and OS based on Ki-67 index in patients with advanced G3 non-small cell gastroenteropancreatic neuroendocrine carcinomas.

2.3.2 To assess the prognostic significance of well differentiated versus poorly differentiated non-small cell gastroenteropancreatic neuroendocrine tumors in relationship to survival and response to treatment.

2.3.3 To assess the agreement in Ki-67 status between that reported by institutional pathologist and that reported by central pathology review.

Rev. 2/17

3. Selection of Patients

Each of the criteria in the checklist that follows must be met in order for a patient to be considered eligible for this study. Use the checklist to confirm a patient's eligibility. For each patient, this checklist must be photocopied, completed and maintained in the patient's chart.

In calculating days of tests and measurements, the day a test or measurement is done is considered Day 0. Therefore, if a test is done on a Monday, the Monday four weeks later would be considered Day 28.

ECOG-ACRIN Patient No. _____

Patient's Initials (L, F, M) _____

Physician Signature and Date _____

NOTE: All questions regarding eligibility should be directed to the study chair or study chair liaison.

NOTE: Institutions may use the eligibility checklist as source documentation if it has been reviewed, signed, and dated prior to randomization by the treating physician.

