12.1 Central Diagnostic and Ki-67 Analysis (MANDATORY, INTEGRATED)

The pathologic diagnosis of G3 gastroenteropancreatic neuroendocrine carcinomas is difficult and diagnostic criteria can be variable between institutions. Therefore, a central pathology review will be conducted on tumor specimens of all patients participating in the study to confirm diagnosis. This will be a retrospective review to ensure that only patients meeting inclusion criteria are considered in the final statistical analysis. Any H&E slides made at the original institution of the patient will be requested along with other diagnostic slides including but not limited to Ki-67, chromogranin and synaptophysin. Pathology reports from the originating institution will also be obtained. Tissue samples will be assessed for tumor histology and mitotic index using standard H&E staining techniques. Ki-67 labeling rate will be evaluated using immunohistochemistry (see methods in Section [12.2.1](#) below). While institutional Ki-67 slides will be evaluated for comparison if available, all patients will have an unstained slide used for Ki-67 analysis. The Ki-67 will be determined by a manual count of at least 500-2000 cells performed on a printed photograph of the stained slide. In addition to manual scoring, computerized imaging analysis will also be conducted on each specimen.

Marker	Primary Ab	Dilution	Company	Secondary Ab	Dilution
Ki-67	Monoclonal	1:100	DAKO	a-mouse	1:200

We will also conduct subset analyses with respect to PFS, OS, and response rate to evaluate the prognostic significance of Ki-67 with regard to these clinical endpoints.

This diagnostic review will be performed under the direction of [name] at Memorial Sloan-Kettering Cancer Center.

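### The Ki-67 status objective (2.3.3) is answered only by an intra-class correlation in an unstated population, so disagreement at the 20% eligibility line may go unreported

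*Combined protocol and SAP*

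**What the plan says.** - **Objective (2.3.3).** "To assess the agreement in Ki-67 status between that reported by institutional pathologist and that reported by central pathology review". The objective gives no cut-point for status.
- **Analysis (9.7.1).** "Concordance between Ki-67 measured centrally versus registering institutions' pathology assessments will also be investigated and reported". The only method named is the next sentence: "Intra-class correlation will be calculated to assess agreement amongst the two continuous measures". Neither sentence names a population, a form of the intra-class correlation (ICC) or a confidence interval. No cross-table, kappa or percent agreement appears.
- **Collection (9.7.1).** "Pathology samples will be collected from all eligible patients".
- **Central review (12.1).** It covers everyone: "a central pathology review will be conducted on tumor specimens of all patients participating in the study to confirm diagnosis", and "all patients will have an unstained slide used for Ki-67 analysis". The same section describes it as a "retrospective review to ensure that only patients meeting inclusion criteria are considered in the final statistical analysis".
- **Eligibility (3.1.3).** A Ki-67 of 20 to 100%, or at least 10 mitoses per 10 high-powered fields. Central review follows randomization, so entry necessarily rests on the institutional reading.
- **Analysis sets (9.2).** The primary set is the randomized patients who are eligible. Toxicity is evaluated in all treated patients whether or not they are eligible.

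**The concern.** Two gaps meet here. First, the objective concerns a status and the statistic concerns a continuous value. A pair of readings of 25% and 12% differs by 13 points, and so does a pair of 80% and 67%. Only the first crosses the 20% line, and an ICC does not separate the two.

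Second, the population is left open in a document whose usual default is the eligible set. If that default is applied, inclusion in the agreement analysis depends partly on the central Ki-67 value, which is one of the two readings being compared. A patient with a local reading of 25%, a central reading of 12% and too few mitoses would be excluded for the very disagreement the objective asks about.

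Section 12.1 justifies central review by variation between institutions in diagnostic criteria. The question a reader would bring to objective 2.3.3 is how often a locally qualifying Ki-67 fails to qualify centrally. Nothing in 9.7 is specified to answer it.

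**Working it through.** **The plan's own figure.** There is none. Section 9.7 gives no ICC target, precision or sample size for agreement. The nearest figure is the ineligibility allowance in 9.2: 80 accrued for 78 eligible, so 2/80 = 2.5% for all reasons together.

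**What each reading of the population does at the 20% line.** Among patients entered on Ki-67 the local value is at least 20%, so the only possible disagreement at 20% is a central value below 20%.

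- *All randomized patients with both readings:* every such patient is counted.
- *Patients eligible on central review:* such a patient is counted only if the mitotic criterion is met. If none meets it, observed disagreement at 20% is zero by construction.

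**How the ICC responds.** The documents give no Ki-67 distribution and no reader error, so these inputs are assumptions:

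- Set A: true Ki-67 normal with mean/SD 55/22, 40/20 or 35/15; reader error SD 5, 10 or 15 points; no systematic reader difference.
- Set B: true Ki-67 = 5 + 95 × Beta(1.3, 1.9) (skewed low) or 5 + 95 × Beta(1.2, 1.2) (symmetric); reader error SD 8 or 12; central reading shifted by 0, -5 or -10 points.

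In both sets, local and central readings are the true value plus independent error, limited to 0–100, and entry requires a local reading of at least 20%. The statistic is the two-way absolute-agreement ICC with k = 2 readings:

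ICC = (MSR − MSE) / [MSR + (k − 1)·MSE + k·(MSC − MSE)/n]

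MSR, MSC and MSE are the mean squares for patients, readers and residual. The runs used 1,000,000 (A) or 400,000 (B) draws per setting.

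| Assumed setting | Central <20%, all entered | ICC, all entered | ICC after removing all central <20% |
|---|---|---|---|
| A: 55/22, error 5 | 1.6% | 0.937 | 0.935 |
| A: 40/20, error 10 | 8.3% | 0.711 | 0.697 |
| A: 35/15, error 15 | 16.6% | 0.373 | 0.345 |
| B: skewed, error 12, shift 0 | 10.7% | 0.727 | 0.709 |
| B: skewed, error 8, shift -10 | 19.6% | 0.756 | 0.734 |
| B: skewed, error 12, shift -10 | 21.8% | 0.641 | 0.614 |
| B: symmetric, error 12, shift -10 | 15.2% | 0.703 | 0.665 |

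Across all settings the share reading below 20% centrally runs from 1.6% to 21.8%. Full removal changes the ICC by between -0.002 and -0.039.

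**Partial removal.** If half of these patients stay eligible through the mitotic count (an assumption), the 10.7% row leaves 0.107 × 0.5 / (1 − 0.107 × 0.5) = 5.7% visible disagreement, and the ICC is 0.721. With the plan's own allowance, removing the 2 lowest central readings of 80 in the 40/20, error 10 setting moves the mean ICC from 0.708 to 0.705.

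**Disagreement elsewhere.** At 55%, the cut mentioned in Section 1.2, it survives removal: 19.9% in all entered patients and 21.6% after removal (40/20, error 10).

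**Precision of the missing proportion.** Exact (Clopper–Pearson) 95% intervals with 80 patients: 8/80 = 10% gives 4.4% to 18.8%; 2/80 = 2.5% gives 0.3% to 8.7%. The real denominator would be the patients with a local Ki-67 of at least 20% and both readings, so somewhat smaller.

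**Mean difference.** In the skewed, error 12, shift 0 setting, the mean central-minus-local difference is -2.1 points in all entered patients and 0.0 after removal, although the readers do not differ. The -2.1 is regression to the mean caused by entry on the local value.

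**The case against.** A reader might infer that the plan computes agreement in eligible patients only and so cannot show the disagreement it asks about. The documents do not support that. The concordance sentences name no population. The sentence about eligible patients in 9.7.1 concerns collection. Material is due within four weeks of randomization (11.1.1) while the review is retrospective and batched, so eligible there cannot mean confirmed by central review. Submission, review and staining cover all patients. Where 9.7.1 narrows a set, as for response to temozolomide and capecitabine, it says so. The final analysis in 12.1 may mean only the primary set. All of this stands. It shows that the population is unstated, not that all randomized patients are specified; against it, 9.2 states explicitly when an analysis ignores eligibility, and does so only for toxicity.

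The objection also holds that an ICC is an accepted measure for continuous readings, that concordance is to be investigated more broadly than the ICC, that a central Ki-67 below 20% does not by itself make a patient ineligible, and that only disagreement at 20% is at risk. Each of these is correct. The broader promise, however, names no second method, and 20% is the Ki-67 line that decides entry.

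A reader might also infer that exclusion would flatter the reported agreement. It would not: the ICC falls slightly in every setting.

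**Conclusion.** The point holds as a gap in specification. Objective 2.3.3 asks about status; 9.7.1 names only an ICC on continuous values and leaves the population open. On a plausible but not explicit reading, patients who disagree at the eligibility line and lack the mitotic criterion would be dropped, and an ICC change of about 0 to -0.04 would not show it.

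The share affected, 1.6% to about 22% of patients entered on Ki-67, rests wholly on assumed distributions, reader errors and reader shifts. The plan's own allowance of 2 ineligible in 80 implies few actual exclusions. It does not bound central disagreement, because the mitotic route can keep such patients eligible.

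This is a laboratory research objective. It does not touch the primary comparison of progression-free survival. It is worth correcting because the correction is cheap and answers the trial's own question.

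**What to change.** In Section 9.7:

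1. Compute objective 2.3.3 on all randomized patients with both an institutional and a central Ki-67 reading, whatever their eligibility on central review.
2. Beside the ICC, report the proportion of patients with local Ki-67 of at least 20% who read below 20% centrally, with an exact 95% confidence interval.
3. State that, because entry is on the local value, only downward disagreement at 20% is observable among patients entered on Ki-67.
4. Treat a cross-table at 55% as optional and exploratory. It is a background cut, neither an eligibility nor a stratification threshold in this trial.
5. If the mean central-minus-local difference is reported, note that entry on the local value pulls it downward through regression to the mean.

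Fix the population and the cut-point before the readings are compared, so that neither is chosen after the result is seen.

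The cost is a few sentences and a few table lines, with no new tissue, patients or significance level. The trial would publish a visible misclassification rate; the ICC itself would not look less favourable.
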